5. STUDY TREATMENTS

5.1. Description of bb1111

BB305 Lentiviral Vector: BB305 LVV is a replication defective, self-inactivating, HIV-1 based LVV, pseudotyped with the vesicular stomatitis virus G envelope protein, carrying the human β -globin gene with a single modification in the coding region at codon 87 ($\beta^{\text{A}87}$ Thr:Gln [$\beta^{\text{A-T87Q}}$]).

bb1111: bb1111 is defined as an autologous CD34+ cell-enriched population from patients with sickle cell disease that contains HSCs transduced with BB305 LVV encoding the $\beta^{\text{A-T87Q}}$ -globin gene, suspended in cryopreservation solution.

5.2. Summary of Treatments to be Performed or Administered

5.2.1. Transfusion Regimen Prior to Drug Product Infusion

For at least 60 days prior to stem cell harvest and continuing through until the start of conditioning, subjects will undergo a transfusion regimen (exchange or simple, as available or needed) to reach a target Hb of 10 g/dL prior to mobilization (and 8 to 10 g/dL prior to conditioning; not to exceed 12 g/dL prior to either mobilization or conditioning) and a pre-transfusion target HbS proportion in the blood of < 30% to reduce the risk of SCD-related complications. The last exchange transfusion must occur within 4 days of start of mobilization, and the HbS proportion in the blood must be < 20% after the last exchange transfusion.

If a subject experiences an SCD-related crisis within 1 month of the start of mobilization, the transfusion regimen will be adjusted, and mobilization will be postponed until the subject is crisis-free for a period of 1 month. In case of iron overload, subjects should be adequately chelated; however, iron chelation must be discontinued at least 7 days prior to stem cell harvest. It may be restarted between completion of the stem cell harvest(s) and admission to the hospital for myeloablation but should be stopped again at least 7 days before initiating myeloablation. Subjects who are not documented to have met these parameters or who have experienced any significant new sickle-related complications within 1 month of the start of mobilization will require additional approval from the Medical Monitor before undergoing mobilization/apheresis.

While simple transfusions may be utilized for the majority of the transfusion period, it is strongly recommended that approximately 24 to 48 hours prior to receiving plerixafor for mobilization, an exchange transfusion (rather than simple transfusion) be performed in an attempt to ensure that the HbS proportion in the blood is < 20%.

5.2.2. Stem Cell Harvest: Bone Marrow

See flow diagram for study design in [Section 3.1](#).

Subjects in Groups A and B1 underwent bone marrow harvest for both manufacture of drug product and back-up cells.

Subjects in Group B2 underwent mobilization with plerixafor and apheresis for collection of back-up cells and exploratory manufacturing development.

Subjects in Group C will undergo mobilization with plerixafor and apheresis for both manufacture of drug product and back-up cells. Group C subjects for whom adequate HSCs are collected to achieve the minimum cell dose but not for rescue, and who are not able to tolerate further plerixafor or did not mobilize well with plerixafor may be offered the option of bone marrow harvest for collection of back-up cells only, provided that drug product manufactured from mobilized cells has met criteria for dispositioning for clinical use. More than 1 bone marrow harvest is allowed if needed to obtain the minimum cell number required for potential rescue, provided that each bone marrow harvest is separated by at least 4 weeks.

Bone marrow harvest should be performed under general anesthesia and using sterile precautions, as per local procedures at the clinical site. Subjects should be monitored for safety as per local procedures for a bone marrow harvest, which must include vital signs and physical exam prior to the procedure and then again prior to discharge. Sickle red cells collected during the harvest procedure are prone to clumping when placed in the hypoxic environment of the bag; therefore, efficient collection, anti-coagulation, and frequent mixing of the collected bone marrow is strongly advised. The bone marrow aspirated should not exceed 20 mL/kg with the aim of obtaining a TNC count of $\geq 1 \times 10^8$ /kg per subject.

Note: as of Protocol Amendment 8.0, bone marrow harvest can no longer be used to collect stem cells for drug product manufacture. Under Protocol Amendment 7.0, each subject in Group B, for whom bone marrow manufacture was planned underwent a minimum of 2 bone marrow harvests, separated by at least 4 weeks. More than 2 bone marrow harvests were allowed if needed to obtain additional cells for manufacture and potential rescue (to meet the cell dose minimum), provided that each bone marrow harvest was separated by at least 4 weeks. When more than 1 bone marrow harvest was used to produce bb1111, then separate drug products were manufactured, release tested and dispositioned from each harvest, but infused on the same day to meet criterion for a single dose.

5.2.3. **Mobilization and Apheresis Procedure**

See flow diagram for study design in [Section 3.1](#).

Subjects in Group B2 underwent mobilization with plerixafor and apheresis for collection of back-up cells prior to undergoing bone marrow harvest for drug product manufacture (with bone marrow harvest for drug product manufacture occurring at least 14 days after the last apheresis session). Subjects in Group B2 who tolerated plerixafor mobilization and underwent successful apheresis with adequate collection of back-up cells were given the option to defer bone marrow harvest for drug product manufacture and instead wait for Group C to open and undergo drug product manufacture using plerixafor-mobilized and apheresed cells.

Subjects in Group C undergo mobilization and apheresis both for collection of back-up cells and manufacture of drug product. Administration of aspirin (80 to 325 mg) is recommended (between 12 hours and 30 minutes prior to initiation of apheresis). Subjects undergoing mobilization/apheresis should remain in the supine position to minimize symptoms (including hypotension) from plerixafor dosing through the end of apheresis each day. Placement of a central venous catheter prior to mobilization is highly recommended to ensure adequate flow rate during apheresis. Platelet count should be confirmed to be $\geq 100 \times 10^9/L$ within 12 hours before the first day of apheresis session in the Cycle. Following plerixafor administration, subjects will be monitored for AEs, e.g., hypotension, syncope, hypoxia, per institutional

practice. Throughout apheresis, subjects will have frequent measures of heart rate, blood pressure, and pulse oximetry, e.g., every 20 minutes for adults, and every 10 minutes for pediatric subjects. If additional apheresis days are required, platelet counts must be confirmed to be $\geq 75 \times 10^9/L$ within 24 hours of subsequent apheresis sessions, prior to administration of plerixafor on that day. If platelet counts do not meet these criteria, mobilization and apheresis should be deferred until platelet counts recover to $\geq 75 \times 10^9/L$. A separate manual on apheresis requirements and recommended parameters will be provided. During the entire time frame leading up to, during and after mobilization and apheresis, close attention should be paid to anticipation and management of pain and anxiety, repletion of electrolyte imbalances, and adequate hydration.

Group B2 (no further enrollment):

If fewer than 1.5×10^6 CD34+ cells/kg are obtained during the initial apheresis session, and the subject has tolerated this session, then the subject must wait for a period of at least 14 days to initiate the next apheresis procedure (Mobilization Cycle 2, Apheresis Day 1; see [Figure 2](#)).

[figure not shown]
During mobilization/apheresis, subjects will be monitored for evidence of plerixafor-associated toxicity.

Plerixafor dosing of initial subjects in Group B2 (enrolled under Protocol Version 6.0) was staggered. Data Monitoring Committee members reviewed the AE profile during plerixafor treatment in mobilization Cycle 1 for the first subject treated in Group B2 and planned to adjudicate on any issues of potential safety significance that could affect determination of DLT before dosing of the second subject with plerixafor. A similar procedure was followed after dosing of the second subject in order to permit dosing of the third subject. The DMC reviewed aggregate safety data in Group B2 after 3 subjects had been dosed and confirmed that there are no safety concerns precluding dosing of subjects in Group C with plerixafor. See also [Section 3.2](#).

Subjects unable to tolerate plerixafor mobilization may be offered bone marrow harvests for collection of back-up cells and for drug product manufacture. Subjects who do tolerate plerixafor mobilization will be given the option of waiting for Group C to open for drug product manufacture.

[Figure 2](#) below depicts the mobilization and apheresis plan for collection of back-up cells from subjects in Group B2. If plerixafor is tolerated, and $\geq 1.5 \times 10^6$ CD34+ cells/kg are collected during Mobilization Cycle 1, then 1.5×10^6 CD34+ cells/kg will be stored for rescue, and any remaining cells will be sent to the Sponsor for exploratory manufacturing development (minimum of 0.5×10^6 CD34+ cells/kg required in shipment).

Figure 2: Mobilization and Apheresis Plan for Back-up Cell Collection (Group B2)

If $< 1.5 \times 10^6$ CD34⁺ cells/kg are collected during the first mobilization cycle, all of these cells will be sent to the Sponsor for exploratory process development work, and a second mobilization cycle may be performed (14 days after the completion of Mobilization Cycle 1), if the subject tolerated the first cycle of mobilization.

After successful mobilization and apheresis of back-up cells, subjects may undergo bone marrow harvests for drug product manufacture at least 14 days after the last apheresis session. See [Section 5.2.2](#) for details surrounding bone marrow harvest. All cells collected from bone marrow will be sent to the transduction facility and utilized for drug product manufacture.

If $< 1.5 \times 10^6$ CD34⁺ cells/kg are recovered in the second cycle of mobilization, as well as in the first, then the subject will be considered an apheresis failure, all recovered cells will be sent to the Sponsor (minimum of 0.5×10^6 CD34⁺ cells/kg required in shipment), and the subject will proceed to bone marrow harvest at least 14 days after completion of the last mobilization/apheresis cycle, for both back-up cell isolation and drug product manufacture.

If ≤ 1 of 3 subjects receiving plerixafor in Group B2 has a DLT during Cycle 1 of mobilization, then Group C may begin dosing with plerixafor.

If > 1 of 3 subjects receiving plerixafor in Group B2 has a DLT during Cycle 1, then a dose of plerixafor ≥ 0.16 and < 0.24 mg/kg may be investigated for mobilization in up to an additional 3 to 6 subjects. Treatment scheme will be as described above.

Group C:

Once the safety and tolerability of plerixafor had been confirmed in Group B2 and regulatory authorities approved the drug product manufacturing process with plerixafor-mobilized HSCs,

[figure not shown]
subjects began dosing with plerixafor in Group C. The first 2 subjects in Group C received drug product infusion in a staggered fashion: neutrophil engraftment was required to occur in the first subject treated in Group C before busulfan conditioning could be initiated for the second subject.

For subjects in Group C, plerixafor dose is 0.24 mg/kg. Apheresis should begin approximately 4 to 6 hours after plerixafor administration. If more than 1 apheresis day is required, platelet counts must be confirmed to be $\geq 75 \times 10^9/L$ within 24 hours of subsequent apheresis sessions, prior to administration of plerixafor on that day. If platelet counts do not meet these criteria, mobilization and apheresis should be deferred until platelet counts recover to $\geq 75 \times 10^9/L$. For subjects undergoing more than 1 mobilization cycle, each cycle must be separated by at least 14 days. Subjects will receive daily plerixafor prior to each apheresis collection. A 3rd day of mobilization and apheresis (to be used for collection of back-up cells only) may be permitted only after prior discussion with the Medical Monitor and if the subject tolerated prior plerixafor and apheresis. If a sufficient number of cells are collected after the first mobilization cycle, no further mobilization/apheresis is required.

For Group C subjects, collection of cells for drug product manufacture will be prioritized over collection of cells for rescue. Subjects for whom back-up cells have already been collected (e.g., participation in Group B2) underwent a separate mobilization/apheresis cycle or bone marrow harvest during which all cells collected were submitted for drug product manufacture.

The schematic below (Figure 3) outlines the plans for plerixafor mobilization and apheresis in Mobilization Cycles 1 and 2 and beyond for subjects in Group C.

Figure 3: Mobilization and Apheresis Plan (Group C)

If plerixafor is tolerated, and $\geq 16.5 \times 10^6$ CD34+ cells/kg are collected after the first apheresis procedure of mobilization cycle 1, then 1.5×10^6 cells/kg will be saved for rescue and the remainder of cells will be sent to the transduction facility for drug product manufacture (as per the Study Operations Manual). If the site is unable to split the collection, then send all cells for drug product manufacture, and collect back-up cells during Apheresis Day 2 of mobilization cycle 1. CD34+ cells for rescue should be stored indefinitely at the clinical site or per local procedures.

If the Apheresis Procedure Day 1 collection of mobilization cycle 1 is $< 16.5 \times 10^6$ CD34+ cells/kg, this collection should be held overnight, at a controlled storage facility at the clinical site (should be shipped immediately to the transduction facility if storage is not possible; minimum of 1.0×10^6 CD34+ cells/kg required in shipment), and the subject should return for Apheresis Procedure Day 2. If the combined yield from Days 1 + 2 of mobilization cycle 1 is $\geq 16.5 \times 10^6$ CD34+ cells/kg, then 1.5×10^6 cells/kg will be saved for rescue, and the remainder of cells will be sent to the transduction facility for drug product manufacture. If the combined yield from Days 1 + 2 is 2.5 to 16.5×10^6 CD34+ cells/kg, then all cells will be shipped for drug product manufacturing, and cells for rescue may be collected during a third day of apheresis in the mobilization cycle, or alternatively, during an additional mobilization cycle that occurs at least 14 days after the last apheresis day of the prior mobilization cycle, at the discretion of the Investigator and Medical Monitor. If the Day 1 + 2 combined yield is $< 2.5 \times 10^6$ CD34+ cells/kg, then up to 1.5×10^6 CD34+ cells/kg will be saved for rescue, with remaining cells shipped for process development, and a second mobilization cycle will be required for collection of cells for drug product manufacturing. If fewer than 1.5×10^6 CD34+ cells/kg were collected during mobilization cycle 1, all cells will be sent to bluebird bio, and collection of cells for both drug product manufacturing and rescue will occur in mobilization cycle 2.

If after drug product manufacture is complete at the central manufacturing facility, a total of $< 3.0 \times 10^6$ CD34+ cells/kg are obtained in the final drug product, or if drug product fails to meet specifications for any reason, subjects may undergo repeat apheresis and manufacture of new drug product, which should occur no sooner than 14 days after completion of the most recent mobilization/apheresis cycle.

Group C subjects for whom adequate HSCs are collected to achieve the minimum cell dose but not for rescue, and who are not able to tolerate further plerixafor or did not mobilize well with plerixafor may be offered the option of bone marrow harvest for collection of back-up cells only, provided that drug product manufactured from mobilized cells has met criteria for dispositioning for clinical use. More than 1 bone marrow harvest is allowed if needed to obtain the minimum cell number required for potential rescue, provided that each bone marrow harvest is separated by at least 4 weeks.

5.2.4. Transduction Process, Storage of Drug Product, Packaging and Labeling, and Traceability

All cell manipulation procedures will be performed in transduction facilities in accordance with Current Good Manufacturing Practices following process-specific procedures.

The subject's CD34+ cells transduced with BB305 LVV are stored and frozen in cryopreservative solution (containing 5% dimethyl sulfoxide) in the vapor phase of liquid nitrogen at the transduction facility until release testing and dispositioning.

In some circumstances, drug product that does not meet the established specification may be administered. This requires justification of medical need as assessed by the Investigator and the Sponsor's Responsible Medical Officer. The subject must be informed and, if applicable, a notification to the appropriate IRBs/ECs and regulatory agency(ies) must occur prior to the start of myeloablative conditioning.

The drug product will be labeled by the transduction facility according to Good Manufacturing Practices, and detailed records will be maintained to allow for accurate traceability of the drug product, to ensure that the drug product is administered to the original donor.

Refer to [Section 5.7](#) (Product Accountability) and the Study Operations Manual (SOM) for details regarding traceability.

Note that samples routinely collected as part of the process of manufacturing the drug product may be used to study the manufacturing process. In particular, these samples may be used to understand how the process may be improved or made more robust. Additionally, these samples may be analyzed if clinically indicated.

If more than 1 stem cell harvest is necessary to produce the minimum cell dose of bb1111, they will be manufactured, release tested, and dispositioned independently as separate drug products, but infused on the same day to meet criterion for a single dose.

5.2.5. Conditioning

5.2.5.1. Busulfan Dosing

Myeloablative conditioning of the subject will be performed using busulfan. Conditioning will only begin after the following criteria are met:

- all drug product lots to be used for the subject have been release tested, dispositioned for clinical use, and stored at the clinical site
- a sufficient number of back-up cells has been collected and stored at the clinical site
- the subject has undergone interim assessments for updated medical history, AE, concomitant medications, physical examination, vital signs, and laboratory tests, all as per the SOE, and continues to meet the eligibility criteria based on these results
- subjects have undergone a transfusion regimen ($Hb > 10 \text{ g/dL}$ and $HbS < 30\%$) and are off HU for at least 2 days and iron chelation for at least 7 days prior to the start of conditioning
- results of conventional cytogenetics (karyotyping) and cytogenetics by FISH from the bone marrow have been received and reviewed by the Investigator and the Medical Monitor; in the presence of a chromosomal abnormality or genetic mutation that does not render the subject ineligible for HSCT per the Investigator's judgment, approval of the Medical Monitor is required before the subject can proceed with conditioning

(see [Section 6.2.11](#)) and subject must sign appropriate informed consent before proceeding with conditioning and treatment with bb1111.

Busulfan will be administered at a starting dose of 3.2 mg/kg/day for 4 consecutive days via IV infusion on Days -6 through -3. The preferred schedule is busulfan via a central venous line (CVL) as a 3-hour infusion once daily for 4 consecutive days for a total of 4 doses. Divided dosing is permitted. In this case, busulfan should be administered as a 2-hour infusion every 6 hours for 16 consecutive doses. For subjects weighing < 35 kg, a q6h dose of 0.8 mg/kg is preferred; for subjects weighing \geq 35 kg, either once daily (qd) or q6h dosing can be used, at the discretion of the Investigator. Please note that the timing of busulfan PK sample collection is based on whether a 2-hour or 3-hour infusion is used.

Clinical sites that use a test dose of busulfan before myeloablation to pre-determine the busulfan pharmacokinetics and predict an optimal dose may do so in this protocol. The recommended test dose of busulfan is 0.8 mg/kg, administered approximately 3 to 10 days before planned initiation of conditioning. Note that clinical sites must be able to measure first and third day busulfan PK, as described below.

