--	--

	
Subjects in Group B2 who tolerated and successfully mobilized with plerixafor for back-up cells, and who had not yet had drug product manufactured with bone marrow harvest, were given the option to delay collection of cells for drug product manufacture until Group C opened, and they could undergo drug product manufacture from cells obtained by a subsequent cycle of plerixafor mobilization.
 
Group C was opened upon (1) confirmation of the safety and tolerability of plerixafor mobilization in Group B2, and (2) regulatory authority approval of the drug product manufacturing process with plerixafor-mobilized HSCs.
 
In Group C, it is planned that all subjects will undergo mobilization with plerixafor and subsequent apheresis to collect HSCs both for drug product manufacture and for cryopreservation of back-up cells for rescue. Subjects who do not tolerate plerixafor or do not effectively mobilize with plerixafor may be offered the option of bone marrow harvest for collection of back-up cells only, provided that drug product manufactured from mobilized cells has met criteria for dispositioning for clinical use.
 
As of Version 8.0 of this protocol, Group C will include adolescent subjects ≥ 12 and < 18 years of age in addition to subjects ≥ 18 and ≤ 50 years of age. It should also be noted that while all Group A subjects and some Group B subjects received drug product manufactured using “Process 1”, all current and future Group C subjects will receive drug product manufactured using an optimized process termed “Process 2”. Treatment with drug product manufactured using Process 2 (versus Process 1) has resulted in increased drug product vector copy number (VCN), peripheral blood VCN, and hemoglobin A containing β^{A-T87Q}-globin (HbA^{T87Q}) levels across multiple bluebird bio-sponsored clinical studies.
 
bb1111 must be release tested and dispositioned for clinical use and stored at the study site before the subject can begin myeloablative conditioning with busulfan.
 
Stage 3 –Myeloablative conditioning and infusion of bb1111
 
The subject’s suitability for transplant will be reconfirmed with clinical laboratory tests (complete blood count [CBC], serum chemistry, liver function tests, and pregnancy test), physical examination, performance status, cytogenetics, and other tests based on institutional requirements. The results of these tests will be reviewed, and availability of the drug product on site and the availability of back-up cells will be confirmed before the site can proceed with conditioning.
 
As described above, a transfusion regimen (exchange or simple, as available and needed) will be continued until the start of conditioning to reach a target Hb (prior to conditioning) of 8 to 10 g/dL (not to exceed 12 g/dL) and a pre-transfusion target HbS proportion in the blood of < 30% to reduce the risk of SCD-related complications; last exchange transfusion must occur within 1 week of start of the conditioning regimen. In the event of pulmonary complications (e.g., acute chest syndrome (ACS), pneumonia) between Screening and the start of conditioning, a pulmonary function test (PFT) must be performed. After resolution of pulmonary complications, and prior to conditioning, PFT results must meet the following requirements:

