Anti-seizure prophylaxis must begin at least 12 hours before initiating busulfan and must continue for at least 24 hours after completion of the 4 days of busulfan administration. All drugs other than phenytoin are allowed for anti-seizure prophylaxis.

After completion of the 4-day course of busulfan, there must be a minimum of 48 hours before drug product infusion. Busulfan levels will be measured 48 and 72 hours after final dose of busulfan for retrospective confirmation of adequate wash-out.

On Day 1, bb1111 will be administered after thawing via IV infusion.

Stage 4 – Follow-up, for approximately 24 months after drug product infusion

Subjects will be followed in the hospital for AEs, and laboratory parameters will be followed to monitor engraftment. The subject may be discharged after neutrophil engraftment occurs ($\geq 0.5 \times 10^9$ ANC/L for 3 consecutive measurements on different days after the initial post-infusion nadir) and the subject is considered medically stable per institutional guidelines.

From drug product infusion through hospital discharge after neutrophil engraftment, subjects are to be medically managed with the goal of maintaining the following hematologic targets:

- Hb 8 to 10 g/dL (not to exceed 12 g/dL), HbS $< 30\%$ and
- platelet count $\geq 50 \times 10^9/\text{L}$.

After discharge, management of transfusions for subjects with SCD will follow the institutional standard of care at the clinical site to achieve total Hb and HbS proportions appropriate for each subject's clinical status. To achieve this, the transfusion program may be progressively reduced

as the contribution of Hb containing $\beta^{\text{A-T87Q}}$ -globin rises. Continued transfusion needs > 6 months post-treatment or any alternative plans should be discussed with the Medical Monitor.

Subjects will be followed in this protocol through the Month 24 Visit. Thereafter, subjects are expected to enroll in a separate, non-interventional, long-term follow-up protocol that will assess safety and efficacy beyond Month 24 for a total of 15 years after drug product infusion. The end of Study HGB-206 will be defined as the last visit for the last subject.

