- Iron chelation therapy: Iron chelation therapy must be discontinued at least 7 days prior to stem cell harvest and conditioning. Phlebotomy or iron chelation therapy using deferasirox or deferoxamine may be restarted at the discretion of the treating physicians no sooner than after discharge from the hospital post-transplant. Deferiprone use is not permitted without prior discussion with and explicit approval of the Sponsor's Medical Monitor. Deferiprone may be used no sooner than 3 months after transplant due to the potential risk of myelosuppression (as per prescribing information for Deferiprone).
- Seizure prophylaxis: Starting at least 12 hours prior to the first dose of busulfan for conditioning, subjects will be treated with anticonvulsants for seizure prophylaxis. The choice of anticonvulsant is at the discretion of the treating physician, but phenytoin is not allowed. Seizure prophylaxis can be discontinued 24 hours after the last dose of busulfan.
- Subjects should not use medications with anti-retroviral activity (such as those used for HIV prophylaxis) from within 1 month of initiating mobilization until after completion of stem cell collection for drug product manufacture.
- pRBC Transfusions: A transfusion regimen will be implemented for at least 60 days before stem cell harvest, and will continue through until busulfan conditioning (exchange or simple, as available or needed) to reach a target Hb of 10 g/dL prior to mobilization (and 8 to 10 g/dL prior to conditioning; not to exceed 12 g/dL prior to either mobilization or conditioning) and a pre-transfusion target HbS proportion in the blood of < 30% to reduce the risk of SCD-related complications. The last exchange transfusion must occur within 4 days of start of mobilization (or within 1 week of start of conditioning regimen), and the HbS proportion in the blood must be < 20% after the last exchange transfusion prior to mobilization, and < 30% after the last exchange transfusion prior to conditioning. Hemoglobin S should be quantified

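### The pre-busulfan checklist in Protocol 5.2.5.1 asks for Hb above 10 g/dL, while four other places set the pre-conditioning target at 8 to 10 g/dL (ceiling 12): an internal inconsistency of minor consequence

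*Protocol*

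**What the plan says.** Protocol 5.2.5.1 introduces its list with the words "Conditioning will only begin after the following criteria are met". The transfusion item in that list reads "subjects have undergone a transfusion regimen ($Hb > 10 \text{ g/dL}$ and $HbS < 30\%$) and are off HU", and goes on to the washout times for hydroxyurea and iron chelation before conditioning.

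The other places that set haemoglobin before conditioning are these:

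- Protocol 5.2.1, which defines the transfusion regimen: "8 to 10 g/dL prior to conditioning; not to exceed 12 g/dL prior to either mobilization or conditioning". The same sentence gives a separate figure for mobilization: "to reach a target Hb of 10 g/dL prior to mobilization".
- Protocol 5.8.2, under pRBC transfusions: "and 8 to 10 g/dL prior to conditioning; not to exceed 12 g/dL prior to either mobilization or conditioning".
- The synopsis and Protocol 3.1, Stage 2, which carry the same rule as 5.2.1.
- The synopsis and Protocol 3.1, Stage 3: "to reach a target Hb (prior to conditioning) of 8 to 10 g/dL (not to exceed 12 g/dL").

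For the next phase, from infusion to hospital discharge, the goal in Protocol 3.1, Stage 4 is again "Hb 8 to 10 g/dL (not to exceed 12 g/dL").

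**The concern.** The list in 5.2.5.1 is the one a site would use as a checklist on the way into myeloablation. Its Hb figure lies on the other side of 10 g/dL from the target set everywhere else. A site working from the list would have to transfuse an on-target subject with sickle cell disease above target, or record that the item was not met. A site working from 5.2.1 would satisfy the regimen but not the literal list. Two sites could therefore manage the same subject differently, each with protocol text to point to.

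What is at stake is clarity of transfusion management immediately before busulfan. No statistical quantity depends on it.

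**Working it through.** No sample size, power or alpha figure is involved, so the check is a comparison of the stated ranges.

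**Inputs**

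- Checklist item (5.2.5.1): Hb > 10 g/dL. The item states no upper limit.
- Pre-conditioning target (synopsis, 3.1, 5.2.1, 5.8.2): 8 ≤ Hb ≤ 10 g/dL.
- Ceiling (same four places): Hb ≤ 12 g/dL.
- HbS: below 30% in all of them, so this part does not conflict.

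**Comparison by band**

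| Hb before conditioning | Literal item (> 10) | Target (8 to 10) | Ceiling (12) |
|---|---|---|---|
| 8 to 10 g/dL | not met | met | met |
| above 10 to 12 g/dL | met | above target | met |
| above 12 g/dL | met | above target | exceeded |

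Item and target: {Hb > 10} and {8 ≤ Hb ≤ 10} have no value in common. Item and ceiling: {Hb > 10} and {Hb ≤ 12} give 10 < Hb ≤ 12, all of it above target.

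Examples: at 9 g/dL a subject is on target but fails the item. At 11 g/dL the subject passes the item and the ceiling but is above target. At 12.5 g/dL the item alone is passed, but 5.2.1 and 5.8.2 bar the value.

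**Could the figure come from elsewhere in the protocol?** The mobilization target is 10 g/dL, not above 10, and the item sits in a list about starting busulfan. The infusion-to-discharge goal is 8 to 10 g/dL with the same ceiling. No other section gives a target above 10. If the sign were meant as ≥, the item and the target would meet only at exactly 10 g/dL.

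**How consistent is the other rule?** It appears six times in four places (synopsis twice, 3.1 twice, 5.2.1 and 5.8.2 once each), in two repeated wordings. The repetitions are not independent evidence of intent, but they agree with each other, and the > 10 figure appears once.

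**The case against.** The best defence is that the figure stands in parentheses after a statement that the subject has undergone a transfusion regimen. The item names no Hb test, sample or timing, so it may be only a loose summary of the regimen and not a measured entry threshold. That reading is plausible, but it does not remove the discrepancy: the regimen is defined in 5.2.1, and the parenthesis gives a different number.

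A second defence is that 8 to 10 g/dL is worded as a target and 12 g/dL is the only stated limit. This stands. A reader might infer that the protocol sets conditions that cannot all be met, so that no subject could be conditioned compliantly. The documents do not support that: Hb above 10 and up to 12 g/dL meets the item and breaks no binding limit. What cannot be done is to meet the item and be at target. Nor does the missing upper limit in the item permit values above 12 g/dL, because the ceiling still applies through 5.2.1 and 5.8.2.

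A third defence is that few or no subjects may still be affected. This also stands. SAP Table 1 shows 36 Group C subjects infused, against approximately 41 planned in Protocol 4.1. The difference of 41 − 36 = 5 is not a count of subjects waiting, and SAP 5.2 already refers to the final study report.

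**Conclusion.** The inconsistency is real and lies in current protocol text. Protocol 5.2.5.1 gives an Hb figure that conflicts with the pre-conditioning target in the synopsis, 3.1, 5.2.1 and 5.8.2. It is a consistency error in an operational threshold, not a questionable design choice, and its severity is minor. Its reach is the transfusion management of subjects not yet conditioned, whose number the documents do not give and which may be zero.

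Two stronger inferences should be resisted.

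- A reader might conclude that subjects already treated were transfused above target or should be counted as deviating. The documents report no such case. Protocol 4.1 also says that Group C includes subjects consented under Versions 7.0, 8.0 and 9.0, and the wording of 5.2.5.1 in those versions is not available.
- A reader might suppose that the results are affected. None of the populations in SAP Table 2 excludes subjects for protocol deviations, so power, the analysis populations and the test of VOE-CR are unchanged.

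The conclusion assumes that 8 to 10 g/dL is the intended figure. The repetition and the definition of the regimen in 5.2.1 make that the likelier reading, but the protocol does not say which number the sponsor meant.

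**What to change.** In Protocol 5.2.5.1, replace the parenthesis with: *target Hb 8 to 10 g/dL, not to exceed 12 g/dL, and HbS < 30%*. The list then agrees with the synopsis, 3.1, 5.2.1 and 5.8.2. If the sponsor did intend a value above 10 g/dL before busulfan, the change has to go the other way, in all four of those places, with a reason given.

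The cost is a one-line wording correction, with no new data, test or sample size and no change to any analysis.
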